## **Treatment**

### **Antimalarial Treatment**

*P. vivax* patients will receive CQ+PQ. The correct drug doses will be determined by the dosing chart (Annex III). All drugs administered in the facility will be under supervision by the staff. Patients will be observed for 60 minutes after treatment for adverse reactions or vomiting. Those patients vomiting their medication within the first 30 minutes will receive a repeat full dose, while those vomiting from 30-60 minutes will receive half dose. Patients who vomit twice will be referred to higher level of care for management with parenteral artesunate therapy and withdrawn from the study. This is standard practice for anti-malarial treatment. All study drugs will be obtained from WHO Ethiopia office through Ethiopian Pharmaceutical Supply Agency.

## Concomitant Treatment

Using standard clinic procedures, clinic personnel will administer supportive treatment to patients as necessary: antipyretics will be given for temperatures  $> 38^{\circ}\text{C}$ . All patients enrolled in the study will be given two additional doses of paracetamol for use at home. Patients/parents/guardians will be instructed in the use and application of tepid sponging and fanning.

## Rescue Treatment

Patients failing in any arm will be treated with second line drug per National Guidelines. Whereas, patients failing with the second line will be administered as of severe malaria criteria that is an indication of treatment failure.

The following are the known efficacy and adverse effects and pharmacokinetics of treatment drugs that will be used in the study:

**Chloroquine Plus Primaquine (CQ+PQ):** Chloroquine Plus Primaquine is a WHO Pre-qualified anti-malarial and FDA approved; WHO certifies the quality, safety and efficacy of the medication, and verifies that the manufacturer complies with WHO Good Manufacturing Practices. CQ+PQ is currently the first line anti-malarial recommended by Ethiopia FMOH for the treatment of uncomplicated falciparum infection. Adverse events are generally mild, most commonly GI (vomiting and diarrhea) and hematologic (anemia and eosinophilia). Its safety will be demonstrated in studies from Ethiopia and Uganda. Chloroquine has a half-life of 30-60 hours (53,54), while primaquine has a elimination half-life of 5-7 hours (54).

## Data Collection Instrument and Procedure

**Data Collection:** Data will be collected and recorded at the health facility by trained study staff members. All data entry will be checked for completeness. Laboratorians may complete brief reports on laboratory findings to share with clinicians who will transfer these results to the case report form of the appropriate patient, and the laboratory results will be entered into database.

**Data Entry, Editing, Handling, Storage and Disposition:** Some open-ended data including the names of specific drugs or diagnoses will be coded prior to data entry. A list of standard codes for these fields will be developed by hand once collection of data is complete. All forms will

then be coded and checked by two different team members.

Systematic routines will be developed to check for data entry discrepancies and range and consistency. If collected on paper, all discrepancies will be resolved by reference to the original checked data collection forms. The final data set will be transformed to statistical software for analysis.

**Storage of Specimens:** Specimens obtained in this study will be saved for the duration of specified testing. Specimens will not be tested for HIV.

**Quality Control/ Assurance:** Site supervisors will check data entry at the end of follow-up for completeness and accuracy of recording. Five percent of the slides will be read by WHO qualified microscopists for quality control.

**Personnel Training:** Three days TOT will be provided for the central team prior to the study. Study clinicians and laboratory personnel are trained and licensed in Ethiopia. They will also receive approximately 1 week additional training to review and familiarize with the study protocol. In addition to technical aspects of specific laboratory techniques and clinical assessments, training will stress the importance of confidentiality and appropriate techniques for obtaining informed consent. The Lab staff will participate in practical exercises. Continued appropriate behavior with regard to informed consent will be reinforced through observation by the supervisor. The staff will include 1-2 laboratory technicians for microscopy and 1-2 staff persons for enrollment and clinical assessments.

**Bias in Data Collection, Measurement and Analysis:** Some bias may be introduced through the fact that both treating clinicians and parents will be aware of which treatment a subject received; as much as possible we will rely on objective measures of improvement (fever resolution, malaria parasitemia) which will be unaffected by knowing the treatment allocation. In addition, the microscopists reading the slides will be blinded to the treatment allocation. Other biases in data collection will be minimized by use of standardized data collection instruments. The principal investigator will ensure that the study protocol is strictly adhered to and that all data are collected and recorded correctly on the case report form. Laboratory and clinical data will be recorded daily on the case report form designed for the study. Data derived from source

documents should be consistent with the source documents, or the discrepancies should be explained. Any change or correction to a case report form should be dated and explained and should not obscure the original entry. All case report forms will be checked for completeness.

After the study has been completed, data will be entered into a database and/or by double independent data entry. The trial data will be stored in a computer database and confidentiality will be maintained.

The principal investigator is responsible for keeping all screening forms, the case report form and the completed subject identification code list in a secure location.

## **Evaluation Criteria**

### **Efficacy and Safety Evaluation**

#### **Classification of Treatment Outcomes**

The primary outcome of this study will be to monitor the efficacy of AL for *P. falciparum* and CQ for *P. vivax* as a routine follow up study and develop baseline and complementary efficacy data for DHA-PPQ against *P. falciparum* and *P. vivax* malaria in Ethiopia.

The classification of treatment outcomes will be based on an assessment of the parasitological and clinical outcome of antimalarial treatment according to the latest guidelines from WHO. Accordingly, all *P. falciparum* and *P. vivax* patients will be classified as having an ETF, LCF, LPF, or ACPR (Annex I).

#### **Safety endpoints**

The incidence of any adverse event will be documented. All patients will be asked routinely about previous symptoms and about symptoms that have emerged since the previous follow-up visit. When clinically indicated, patients will be evaluated and treated appropriately. All adverse events will be recorded on the case report form. Serious adverse events will be reported to all relevant authorities.

#### **Clinical Evaluation**

All patients will be evaluated clinically as described below.

#### **Physical Examination**

A standard physical examination will be performed at baseline (day 0 before dosing) and on days 1, 2, 3, 7, 14, 21, 28, 35, and 42. A complete medical history, demographic information, and contact details will be recorded at baseline.

### Body Weight

Body weight will be recorded on day 0 to the nearest kilogram on a scale or on a hanging scale for young children. The scales will be properly calibrated. Patients should not wear excessive clothing while being weighed as this can overestimate their true weight. All young children should only wear undergarments while being weighed. The screening weight will be used to satisfy the inclusion or exclusion criteria for weight and nutrition status as well as to calculate the dose (number of tablets) to be administered. The reliability of the scales will be verified before the study begins and checked at regular intervals.

The circumference of the left mid-upper arm will be measured, at the mid-point between the elbow and the shoulder and will be recorded to the nearest 0.2 cm. Oedema will be assessed by thumb pressure for 3 seconds on the dorsal surface of both feet.

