#### Exclusion Criteria

- ♣ Severe malaria with complication sign and symptoms (see Annex I)
- ♣ Signs or symptoms of severe malnutrition, defined as weight-for-age  $\leq$  3 standard deviations below the mean, symmetrical edema involving at least the feet, or mid-upper arm circumference <100 cm for children less than five years of age (NCHS/WHO normalized reference values; see Annex I)
- ♣ Mixed plasmodium infection
- ♣ Severe anemia, defined as hemoglobin (Hb) < 8 g/dl

- ♣ Presence of febrile conditions caused by diseases other than malaria (e.g. measles, acute lower respiratory tract infection, severe diarrhea with dehydration)
- ♣ Serious or chronic medical condition (e.g. cardiac, renal, hepatic diseases, sickle cell disease, HIV/AIDS)
- ♣ Positive pregnancy test or breastfeeding
- ♣ Unable or unwilling to take contraceptives for women of child-bearing age
- ♣ Children weighing less than 5 kilograms
- ♣ History of hypersensitivity reaction to any medication tested or used as an alternative treatment
- ♣ Participants with history of prolonged QT conditions
- ♣ Taking regular medication, which may interfere with antimalarial pharmacokinetics or efficacy (see Annex VII)?

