## **Screening and Enrollment Procedures**

### **Screening**

Screening for eligible patients at the study sites will be done in the following fashion:

1. All patients over 6 months with temperature  $\geq 37.5^{\circ}\text{C}$  or a history of fever in the last 48 hours will have screening blood smear performed as per the national diagnosis and treatment guidelines at the health centers. Patients with microscopy confirmed *P. falciparum* or *P. vivax*, age greater than 6 months, and living within 5 km of the health center will be screened.
2. For all facilities, if the patient meets the screening criteria and the patient or the parent or guardian consents to enrollment, they will be assigned a consecutive, unique number that will become the patient's study number and will be used to identify all forms and blood samples from that patient. Enrollment will be conducted by a staff member not involved in

the clinical assessment of the participant to ensure that consent is freely given.

3. A screening form containing demographic, clinical, and laboratory information will be started on each smear positive patient, thus allowing for appropriate tracking of each patient through the screening procedure.
4. The patient's body weight will be measured to the nearest kilogram, using a hanging scale for weighing young children, or a floor scale for large children/ adults and recorded on the demographic form. The circumference of the left upper mid-upper arm will be measured at the mid-point between the elbow and shoulder, and will be recorded to the nearest 0.2 cm. Edema will be assessed by thumb pressure for 3 seconds on the dorsal surface of both feet.

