## ANNEXES

## Annex 1. Patient Screening Form

## Patient Screening Form

STUDY SITE CODE: \_\_\_\_\_

TREATMENT GROUP: \_\_\_\_\_

1. Names:	2. Date: (dd/mm/yy) ____ / ____ / ____	3. Weight (kg):
4. Age*: years _____ months. _____	5. Gender: M _____ F _____	

1.	Patient aged > 6 months /Both sex	Yes:	No:
2.	P. vivax mono-infection asexual parasites/ $\mu$ l Pv 250-100,000/ $\mu$ l	Yes:	No:
3.	Body weight > 5 kg	Yes:	No:
4.	Patient with fever or history of fever in the previous 24 hours	Yes:	No:
5.	Non-pregnant or breast-feeding female	Yes:	No:
6.	Ability to swallow oral medication	Yes:	No:
7.	Residents living within 5 km radius of the health centre and agree to return for all scheduled follow up visits	Yes:	
8.	Willing to give informed consent	Yes:	No:
9.	Evidence of concomitant febrile illness If "YES", indicate illness. If "NO", leave blank. 
 
☐ Pneumonia/RTI      ☐ Measles
 
☐ Otitis Media      ☐ UTI
 
☐ Gastroenteritis      Other:
 
	Yes:	No:
10.	Evidence of severe malaria / danger signs If "YES" indicate criteria. If "NO", leave blank. 
 
☐ Unarousable coma (if after convulsion, > 30 min)
 
☐ Repeated convulsions (> 2 within 24 h)
 
☐ Recent convulsions (1-2 within 24 h)
 
☐ Altered consciousness(confusion, delerium,, coma)
 
	Yes:	No:

	
 
ə Lethargy
 
ə Unable to drink or breast feed
 
ə Vomiting everything
 
ə Unable to stand/sit due to weakness
 
ə Severe anaemia (Hb < 5.0 g/dL)
 
ə Respiratory distress (laboured breathing at rest)
 
ə Jaundice (yellow colouring of eyes)
 
		
11.	Known hypersensitivity to AL/CQ/DP	Yes:	No:

If any of the responses fall into the shaded area, exclude the patient from the study

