## ANNEX 5: Drug Dosing and Regimens

All patients will be weighed to determine the accurate weight-based dose for all drugs.

- **Chloroquine:** Total of 25mg base per kg over 3 days (10 mg base/kg on Days 1 and 2, and 5 mg base/kg on Day 3). 500 mg tablets. We will use the syrup (10mg/ml) formulation for children < 4 years of age, if available.

Weight (kg)	Age	Day 1	Day 2	Day 3
5–6	<4 mo	¼ tablet (5 ml syrup)	⅛ tablet (5 ml syrup)	⅛ tablet (2.5 ml syrup)
7–10	4–11 mo	¼ tablet (7.5 ml syrup)	¼ tablet (7.5 ml syrup)	¼ tablet (5 ml syrup)
11–14	1–2 yrs	½ tablet (12.5 ml syrup)	½ tablet (12.5 ml syrup)	¼ tablet (7.5 ml syrup)
15–18	3–4 yrs	½ tablet (15 ml syrup)	½ tablet (15 ml syrup)	½ tablet (15 ml syrup)
19–24	5–7 yrs	¾ tablet (20 ml syrup)	¾ tablet (20 ml syrup)	½ tablet (15 ml syrup)
25–35	8–10 yrs	1¼ tablet	1¼ tablet	½ tablet
36–50	11–13 yrs	1½ tablet	1½ tablet	1 tablet
> 50	14+ yrs	2 tablet	2 tablet	1 tablet

--	--	--	--	--

**Primaquine:** 7.5 mg base tablet. Medication given as 0.25mg/kg daily for 14 days in people with normal G6PD levels. In people with G6PD deficiency, 0.75 mg/kg (45 mg) once a week for 8 weeks.

Body Weight (kg)	Single dose of primaquine (mg base)
5 to 10	Weight-based using extemporaneous preparation as outlined by Sanofi
10 to < 25	3.75
25 to <50	7.5
50 to 100	15

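### Two weight cut-points conflict as written: the screening form's 5 kg limit contradicts the eligibility criteria, and a 10 kg child falls in two primaquine dose rows

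*Combined protocol and SAP*

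**What the plan says.** The Body Weight section sets the resolution: "Body weight will be recorded on day 0 to the nearest kilogram on a scale or on a hanging scale for young children". Screening, item 4, repeats it: "The patient's body weight will be measured to the nearest kilogram". The Body Weight section then gives this value its uses: "The screening weight will be used to satisfy the inclusion or exclusion criteria for weight and nutrition status as well as to calculate the dose", adding that dose here means a tablet count. Arm circumference, in the same section, "will be recorded to the nearest 0.2 cm".

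The lower weight limit appears in three places:

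- The Inclusion Criteria require at least 5.0 kg.
- The Exclusion Criteria list "Children weighing less than 5 kilograms", which agrees with that.
- Annex 1, Patient Screening Form, item 3, asks for "Body weight > 5 kg", which does not.

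On dosing, Annex 5 says: "All patients will be weighed to determine the accurate weight-based dose for all drugs". Primaquine is set at 0.25 mg/kg a day for 14 days in patients with normal G6PD. In its table, the 5 to 10 kg row calls for an individually prepared, weight-based dose under a manufacturer's outline that is not reproduced. The next row runs from 10 kg to under 25 kg and gives a fixed 3.75 mg.

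**The concern.** Both faults arise when staff follow the documents as printed. At the lower limit, the form used at the point of enrolment and the protocol's own criteria give opposite answers for the same recorded weight of 5. A child can be correctly eligible and still be refused, or be enrolled in line with the criteria list while the form says no. At 10 kg, two staff members can read the same table and give doses that differ by half.

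Whole-kilogram recording did not create either conflict, but it widens both. Instead of touching only children of exactly 5.0 or 10.0 kg, each conflict covers a band one kilogram wide. The stakes are consistent eligibility and a consistent primaquine dose in the smallest children, not the trial's main result.

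**Working it through.** **Inputs.** Weight resolution is 1 kg (Body Weight; Screening, item 4). The limit is at least 5.0 kg (Inclusion Criteria), exclusion is below 5 kg (Exclusion Criteria), and the form requires more than 5 kg (Annex 1, item 3). Primaquine is 0.25 mg/kg a day for 14 days, with the two table rows described above (Annex 5). I assume ordinary rounding, so a recorded weight w covers true weights from w - 0.5 to just under w + 0.5 kg.

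**Do the table's fixed doses match the stated target?** 3.75/0.25 = 15 kg, 7.5/0.25 = 30 kg and 15/0.25 = 60 kg. Each lies inside its own row (10 to under 25, 25 to under 50, 50 to 100 kg). This supports reading the table's single-dose column as the daily dose, although the annex does not say so.

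**Step 1: the 5 kg limit.**

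| True weight (kg) | Recorded | Criteria list | Screening form |
|---|---|---|---|
| 4.5-4.99 | 5 | admits, though below the limit | refuses |
| 5.0-5.49 | 5 | admits | refuses, though eligible |
| 5.5-6.49 | 6 | admits | admits |

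In effect the criteria list operates at 4.5 kg and the form at 5.5 kg. At exactly 5.0 kg they disagree on any scale, so that part does not depend on rounding.

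**Step 2: the 10 kg rows.**

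- Weight-based row: 0.25 × 10 = 2.5 mg a day; over 14 days, 14 × 2.5 = 35 mg.
- Fixed row: 3.75 mg a day, or 3.75/10 = 0.375 mg/kg; over 14 days, 14 × 3.75 = 52.5 mg.
- Ratio: 3.75/2.5 = 1.50, a 50% difference.

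True weights of 9.5-10.49 kg are all recorded as 10 and all meet this choice.

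**Step 3: rounding on its own.** If the recorded weight sets the weight-based dose, the relative error is (recorded/true) - 1.

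- Recorded 5: 5/4.5 gives +11.1%; 5/5.49 gives -8.9%.
- Recorded 7: 7/6.5 gives +7.7%; 7/7.49 gives -6.5%.
- Recorded 10: 10/9.5 gives +5.3%; 10/10.49 gives -4.7%.
- Weighing to 0.1 kg: 0.05/5 = 1.0% at 5 kg and 0.05/10 = 0.5% at 10 kg.

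For comparison, the fixed 3.75 mg row spans 3.75/10 = 0.375 mg/kg (+50% against 0.25) to 3.75/24.9 = 0.151 mg/kg (-40%).

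For weight-for-age, the documents give no SD. On an assumed SD of 0.7-1.5 kg, an error of 0.5 kg is 0.5/1.5 = 0.33 to 0.5/0.7 = 0.71 SD. Weighing to 0.1 kg makes it 0.05/1.5 = 0.03 to 0.05/0.7 = 0.07 SD.

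**Step 4: who is affected.** Patients must be older than 6 months. The chloroquine chart in Annex 5 pairs 5-6 kg with under 4 months and 7-10 kg with 4-11 months. Children near 5 kg should therefore be rare, whereas a 10 kg child is entirely plausible.

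**The case against.** The strongest case against is that this is housekeeping. The sample is 88 patients of any age above 6 months, very few will weigh close to 5 kg, and whole kilograms suit the chloroquine chart, whose rows are in whole kilograms. The other primaquine rows include their lower bound and exclude their upper one, so a careful reader might place 10 kg in the 3.75 mg row by analogy. All of that is fair and limits the weight of the point. It does not remove the conflict: the form and the criteria still disagree, and the 5 to 10 kg row is printed without an exclusive upper bound.

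A reader might go further and infer that whole-kilogram weighing is itself the main defect and misdoses infants by up to 11%. The documents do not support that. The tablet wording in the Body Weight section does not clearly reach a prepared liquid or powder, and the weight steps of that preparation are not given. The 11% figure needs a true weight of 4.5 kg, a child who should not be enrolled; at recorded weights of 7-10 kg the error is about 5-8%, well inside the spread that the fixed row already accepts.

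A reader might also infer that malnourished children will be misclassified to an important degree. That rests on an assumed SD, and nothing shows how many children lie near the limit. Oedema and arm circumference are further signs of malnutrition. The latter is printed as "mid-upper arm circumference <100 cm for children less than five years of age", presumably a unit slip. Read literally, it would exclude practically every child under five; that is a separate correction.

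**Conclusion.** The point holds for the two cut-points. The form contradicts the criteria at 5 kg: it turns away eligible children of 5.0-5.49 kg, where the criteria list would let in children of 4.5-4.99 kg. Annex 5 permits two primaquine doses at 10 kg that differ by 50%. The 2.5 mg figure assumes that the weight-based row follows the stated 0.25 mg/kg, and the 14-day totals assume that the table gives a daily dose in a patient with normal G6PD.

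Whole-kilogram recording aggravates both faults, and finer weighing is worth having, but it is a secondary improvement. Nothing here alters the sample size or the primary efficacy estimate, and no safety consequence can be shown from the documents. This is a minor correction, worth making because it costs almost nothing.

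**What to change.** 1. **Annex 1, item 3:** require a body weight of at least 5.0 kg. This is one form item and needs no equipment. On its own it aligns form and criteria, but children of 4.5-4.99 kg could still be admitted while weight is taken to the whole kilogram.
2. **Annex 5, primaquine table:** make the rows non-overlapping, preferably 5 to 10 kg and then above 10 to under 25 kg, so that a 10 kg child receives the stated 0.25 mg/kg. The cost is individual preparation for those children. The alternative, 5 to under 10 kg, follows the pattern of the other rows and avoids that preparation, but gives 0.375 mg/kg at 10 kg. Either removes the ambiguity.
3. **Minor addition, Body Weight and Screening, item 4:** record weight to 0.1 kg in young children, and use that single value for the 5.0 kg limit, weight-for-age and any weight-based primaquine dose. The lowest true weight that can pass as 5.0 kg then becomes 4.95 kg. The cost is scales graduated to 0.1 kg and one line in Annex 5 saying how weights are rounded for the whole-kilogram chloroquine rows; rounding to the nearest kilogram leaves those doses as they are.

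None of this narrows the spread within the fixed 3.75 mg row. Under items 2 and 3 together, a child of 10.1 kg would receive 3.75/10.1 = 0.371 mg/kg.

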### Body Temperature

Axillary temperature will be measured at baseline (day 0 before dosing) and on days 1, 2, 3, 7, 14, 21, 28, 35, and 42. Temperature will be measured with a thermometer that has a precision of 0.1 °C. Temperature will also be measured as clinically indicated. If the result is < 36.0 °C, the measurement will be repeated. The same route will be used throughout the study. The quality of the temperature-taking technique and the thermometers will be assessed regularly.

### Laboratory Examination

**Microscopic blood examination:** thick and thin blood smears will be taken from all participants and prepared on the same slide for detection of parasites at all time-points during the 42-day follow-up period. Two smears will be prepared in each case; the first will be stained rapidly with 10% Giemsa for 10–15 min for initial screening and examined by light microscopy immediately. On day 0, in order to rapidly confirm adherence to the lowest parasite density considered for enrollment, initial screening of patients will be made in 10% Giemsa-stained thick film after counting at least 1 parasite for every 6-8 WBCs, which corresponds to approximately 1000 parasites/ $\mu$ l.

The second one will be stained slowly with 3% Giemsa 45–60 min to be examined later by an experienced technician to provide definitive parasite count and speciation. The below formula will be used to determine parasite density.

$$\text{Parasite density (per } \mu\text{l)} = \frac{\text{number of parasites counted} \times (6000-8000)}{\text{Number of leukocytes counted} \approx 200}$$

Two experienced laboratory technicians will examine slides independently. Parasite densities will be calculated from thick blood smears by counting the number of asexual parasites against 200 WBC. If the count is <10 parasites/200 WBC, at least 500 WBC will be counted. A thick blood smear will be declared negative if no parasites are seen in 1000 WBCs and mixed infection has been excluded in 100 fields on thick film. Gametocytes will be detected and counted in thick film. Thin blood smears will be examined to determine parasite species. Gametocytes will be counted in thick blood films against 2000 WBCs.

Two qualified microscopists will read all the slides independently, and parasite densities will be calculated by averaging the two counts. Blood smears with discordant results (differences between the two microscopists in species diagnosis, in parasite density of > 50% or in the presence of parasites) will be re-examined by a third, independent microscopist, and parasite density will be calculated by averaging the two closest counts.

**Hemoglobin:** The hemoglobin concentrations will be measured using a portable spectrophotometer (HemoCue®, Anglom, Sweden), on days 0, 14, 28, and 42.

**Blood sample collection:** To minimize discomfort to the patient due to repeated finger pricks, all samples will be collected from a single prick. Two slides, hemoglobin and two to three drops of blood will be collected on Whatman filter paper and 100µl of blood using capillary tube will be collected during enrolment. Blood spots will be collected only on enrollment, on day 3, 7 and during treatment failure (Annex: VI)

Specimens will be labeled anonymously (study number, day of follow-up, date), kept in individual plastic bags with desiccant pouches and protected from light, humidity and extreme temperature until analyzed. Samples will be kept in freezers in the study sites and eventually transferred to EPHI, to be frozen at -20°C.

**Pregnancy Test:** Female patients of child-bearing age, defined as those who menstruate or are aged over 18 years (depending on situations), will be asked to take a urine pregnancy test before enrolment in the study. They will also be asked to take a urine pregnancy test on day 28/42 or on

early withdrawal from the study. Female participants of child-bearing age who are sexually active to control pregnancy for the duration of the study.

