## Statistical Analysis

Every data from recruited patients will be imported into the WHO Excel sheet (double entry) which is designed for analysis of therapeutic efficacy study data. Data will be also entered in to IBM SPSS (version-26) software to calculate descriptive statistics (mean, median, standard deviations, range). Independent sample t-test will be used to compare baseline temperature and parasitemia between children and adults; mean blood Hb level at D0, D14, D28 and D42 between patients with parasitemia  $\geq 10,000$  and  $< 10,000/\mu\text{l}$  blood. Non-parametric (median) test for independent sample will be used to compare D1 parasitemia between children and adults and paired sample t-test will be used to compare mean Hb level between D0 and D14, D0 and D28, D14 and D28, D0 and D42, D28 and D42. All comparisons will be performed at 95% CI and significance level of 0.05.

Kaplan Meier (K-M) survival analysis and per protocol (PP) analysis will be used for estimation of primary outcomes and PP analysis method will be used to analyze secondary outcomes. The K-M survival analysis method provides better approximation of cure rates as it incorporates probabilities for censored data (incomplete observations due to LFU and withdrawals) in to the analysis. The WHO excel sheet is especially designed for estimation of cure rate based on K-M survival estimator analysis method.

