**Early Treatment Failure (ETF)**

- Danger signs or severe malaria on day 1, day 2 or day 3 in the presence of parasitemia;
- Parasitemia on day 2 higher than on day 0, irrespective of axillary temperature;
- Parasitemia on day 3 with axillary temperature  $\geq 37.5$  °C;
- Parasitemia on day 3  $\geq 25\%$  of count on day 0.

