#### **Day 3, Day 7, Day 14, Day 21, Day 28, Day 35, and Day 42:**

---

- Clinical assessment — referral in case of severe malaria/danger signs
- Measurement of axillary temperature
- Blood sampling for blood smears and filter paper
- Alternative treatment in case of treatment failure
- Hemoglobin/hematocrit (Day 0, Day 14, Day 28, Day 42)

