#### **Any other day:**

- Clinical assessment — referral in case of severe malaria/danger signs

- Measurement of axillary temperature
- Blood sampling for blood smears and filter paper
- Hemoglobin/hematocrit if indicated clinically
- Alternative treatment in case of treatment failure

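### No haemoglobin is scheduled between day 0 and day 14, so transient or symptomless falls on days 1 to 13 are found only by clinically prompted testing

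*Combined protocol and SAP*

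**What the plan says.** - Laboratory Examination sets haemoglobin "on days 0, 14, 28, and 42". Annex 8 repeats it ("Hemoglobin/hematocrit (Day 0, Day 14, Day 28, Day 42"), Annex 9 marks the same four days, and Statistical Analysis uses only those days ("mean blood Hb level at D0, D14, D28 and D42", plus paired t-tests between them, including D0 against D14).
- For unscheduled returns, Annex 8 allows "Hemoglobin/hematocrit if indicated clinically", and Annex 9 marks haemoglobin in its column for other days.
- Annex 5 gives the primaquine course: "Medication given as 0.25mg/kg daily for 14 days in people with normal G6PD levels". Patients with G6PD deficiency get a weekly dose for eight weeks instead.
- The drug description under Rescue Treatment says: "Adverse events are generally mild, most commonly GI (vomiting and diarrhea) and hematologic (anemia and eosinophilia".
- Safety Assessment finds adverse events by asking the patient. The coded adverse-event list on the case record form has no anaemia item; it has weakness, dizziness and an open category.
- Blood sample collection states that "all samples will be collected from a single prick". Annex 9 has a blood slide at every visit and filter paper on days 3 and 7.

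**The concern.** The protocol names a haematological harm as common and makes the primaquine regimen depend on G6PD status, but schedules no G6PD test in the screening, enrolment or follow-up sections. Haemoglobin is then the only scheduled laboratory measure of red-cell safety, and it is absent for the first two weeks of follow-up, when most or all of the daily course is taken. Questioning will not reliably find a moderate fall that causes no symptoms. If such a fall recovers by day 14, neither the adverse-event record nor the haemoglobin analysis will show it. What is at stake is the safety description, not the efficacy estimate.

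**Working it through.** The plan gives no figure to reproduce here; the check sets visit days against dosing days.

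**Inputs.** Scheduled haemoglobin days H = {0, 14, 28, 42} (Laboratory Examination, Statistical Analysis, Annexes 8 and 9, all in agreement). Visits: 0, 1, 2, 3, 7, 14, 21, 28, 35, 42 (Annex 9). Primaquine: 14 daily doses, or 8 weekly doses (Annex 5). Start day s: not stated for primaquine. Enrollment and Follow-up speaks only of treatment on day 0 with returns on days 1 and 2, so I assume s = 0 to 3 and show the range.

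**Step 1, the gap.** Between days 0 and 14 there are 14 − 0 − 1 = 13 days (1 to 13) without a scheduled value. Four visits fall in that gap: days 1, 2, 3 and 7.

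**Step 2, daily course.** Doses run from day s to day s + 13. Count the members of H after the first dose day and up to the last:

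| Start s | Last dose day | Scheduled haemoglobin on treatment |
|---|---|---|
| 0 | 13 | none (day 14 is 14 − 13 = 1 day after the last dose) |
| 1 | 14 | day 14 only, the last dose day |
| 2 | 15 | day 14 only, 1 day before the last dose |
| 3 | 16 | day 14 only, 2 days before the last dose |

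Days 1, 2, 3 and 7 are unmeasured in every row.

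**Step 3, weekly course.** Dose days are s + 7k, k = 0 to 7. For s = 0 these are 0, 7, 14, 21, 28, 35, 42 and 49, so days 14, 28 and 42 are all on treatment. The same three values are on treatment for s = 1, 2 or 3 (last doses on days 50, 51 and 52). Even here, with s = 0, the first reading after day 0 comes on the third dose day.

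**Step 4, what D0 against D14 can show.** Apart from measurement error, a patient's lowest haemoglobin over days 0 to 14 is at most the day 14 value. So (day 0 value − lowest value) ≥ (day 0 value − day 14 value). The planned comparison gives a lower bound on the largest fall, with equality when day 14 is the lowest point. The documents give no haemoglobin time course, so the size of any shortfall cannot be computed.

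**Step 5, with readings added on days 3 and 7.** For a daily course from day 0, scheduled on-treatment values go from 0 to 2 (days 3 and 7), and the longest interval between readings up to day 14 drops from 14 days to 14 − 7 = 7. Extra tests: 88 × 2 = 176, against 88 × 4 = 352 now scheduled, if everyone attends every visit.

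**The case against.** The schedule is internally consistent and matches the analysis. The study estimates efficacy from treatment failure, and extra readings change neither the sample size nor the Kaplan-Meier analysis. That stands, and it limits the point to safety information.

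Four stronger readings are tempting, and the documents do not support them.

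- *Every scheduled haemoglobin lies outside primaquine treatment.* This needs a day 0 start, which is not stated, and the daily course. A start on days 1 to 3, or the weekly course, makes it false.
- *On-treatment falls are missed.* Symptomatic falls can be tested on request, patients are assessed at each visit and told to return on any day, and a fall that persists would show on day 14. Only transient or symptomless falls are exposed. The prompted-test line is written for unscheduled days; I read it generously, as covering a clinician's request at a scheduled visit too.
- *The D0 to D14 comparison understates the largest change.* Only *may understate* is supported, because no section says when the lowest value occurs.
- *Early treatment failure cannot be classified.* Annex 4 counts "Danger signs or severe malaria on day 1, day 2 or day 3 in the presence of parasitemia", and low haemoglobin is one severe-malaria criterion. But severe malaria is sought by clinical assessment at each visit. Annex 6 requires a parasite count above 10,000 alongside the low haemoglobin, and it also lists glucose, lactate, creatinine and bilirubin, none of them scheduled.

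Nor should new readings be used to reclassify outcomes, because the limits they would be judged against conflict. Emergency Care and Annex 1 use below 5 g/dl without an age or parasite condition. Annex 6 uses below 5 g/dl in children under 12 and below 7 g/dl in adults, with the parasite condition.

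**Conclusion.** The concern holds in limited form. Thirteen days, containing four attended visits, have no scheduled haemoglobin. If the daily course starts on day 0, no scheduled value falls after the first dose and up to the last; if it starts on days 1 to 3, one does, at or near the end. The weekly course has three. Detection of a transient or symptomless fall on days 1 to 13 rests on prompted testing, and the D0 to D14 comparison is only a lower bound on the largest fall.

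This rests on the unstated start day, shown here for days 0 to 3. How often such falls occur, or how deep they are, cannot be derived from the documents. I rate it as something the sponsor should change: a cheap gain in safety information with no bearing on the primary estimate.

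**What to change.** 1. Add a haemoglobin reading at the existing day 3 and day 7 visits, in Laboratory Examination, Annex 8 and Annex 9, from the finger-prick already made for the slide and filter paper.
2. In Statistical Analysis, add two descriptive safety summaries per patient: the lowest value after day 0 and the largest fall from day 0. Give the number of readings behind each, since a minimum over more noisy readings tends to be lower even without true change. Add no tests, and do not use these readings to reclassify treatment outcomes.
3. State the primaquine start day. Annex 9 shows drug only on days 0 to 2, and the primaquine table in Annex 5 is headed as a single dose although the text gives a course; these must be reconciled.
4. Reconcile the severe-anaemia limits (Emergency Care and Annex 1 against Annex 6) and the entry limits (below 8 g/dl in Exclusion Criteria against below 5 g/dL in Enrollment and Follow-up). Which value applies is for the clinical team.

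The cost is about 176 portable tests and two more form entries per patient, with no extra visit, prick or staff. No treatment rule is proposed.
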